- 24) Additional factors that render the participant unable to complete the study, as judged by the investigator

Investigational medicinal products, dosages and administration:

There will be two separate study kits for study drug 1 and 2

Investigational medicinal product 1 (IMP1) and dosing: Varenicline 1 mg x 2 p.o. daily

The pharmaceutical formulation will be encapsulated tablets for oral use.

Each patient kit will contain blister packed varenicline, packed in secondary packaging.

Varenicline will be escalated from 0.5 to 2 mg daily during the first week.

Day 1-3: 0.5 mg or corresponding placebo capsules once daily

Day 4-7: 0.5 mg or corresponding placebo capsules twice daily

Day 8-91: 1 mg or corresponding placebo capsules twice daily

No dose adjustment of varenicline is allowed in the study.

Investigational medicinal product 2 (IMP 2) and dosing: Bupropion SR 150 mg x 2 p.o. daily

The pharmaceutical formulation will be encapsulated sustained release (SR) tablets for oral use.

Each patient kit will contain blister packed bupropion, packed in secondary packaging.

Bupropion will be escalated from 150 to 300 mg daily during the first week.

Day 1-7: 150 mg or corresponding placebo capsules once daily

Day 8-91: 150 mg or corresponding placebo capsules twice daily

No dose adjustment of bupropion is allowed in the study.

Dosages: The IMPs will be distributed at 7 occasions: Day 0, Day 7, Day 21, Day 35, Day 49, Day 63 and Day 77. The doses and route of administration for varenicline and bupropion are those approved and recommended as oral formulations for smoking cessation. (Bupropion is registered for major depression in two dose levels, 300 mg daily, as used in the present study and in a lower dose of 150 mg daily.)

Double blind treatment phase (Week 1-Week 13)

The trial comprises 9 study visits over 91 days: Screening visit, Day 0 (randomization), Day 7, Day 21, Day 35, Day 49, Day 63, Day 77 and Day 91. The total duration of the study for one participant will be 13 weeks (91 days). Week 1 is dose escalation. Steady state dose period is Week 2 - Week 13.

Randomization

Randomization will be carried out according to block randomization.

Eligible subjects will be randomized in a 1:1:1:1 ratio to one of the following treatments:

- 1) Varenicline + Bupropion SR
- 2) Varenicline + Placebo
- 3) Bupropion SR + Placebo
- 4) Placebo + Placebo

Stratification

No partitioning other than the intervention will be used.

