4. STUDY POPULATION

4.1. Inclusion criteria

- 1) Signed informed consent
- 2) Blood alcohol level below <0.1‰ (0.1 g/L) at signing informed consent
- 3) 25-70 years of age at screening
- 4) Moderate and severe AUD according to DSM-V (meeting ≥4 out of 11 criteria)
- 5) B-PEth levels of ≥0.5 µmol/L at screening visit (visit 1) as defined by at least 2 HDD per week on a typical week.
- 6) Continuous high alcohol consumption over the last 3 months prior to screening
- 7) Available phone number for contact
- 8) Ability to speak and write in Swedish

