8. STATISTICS

8.1. Sample size calculation

The power analysis is based on two independent primary hypotheses;

- B-PEth differs significantly between VAR and BUP in combination and alone versus placebo
- Proportion of heavy drinking days (HDD) differ significantly between VAR and BUP in combination and alone versus placebo

Concerning B-PEth, we assume that we can use ordinary t-tests based on normal distribution, with $\alpha=0.025$, $1-\beta=0.80$ and using a standard deviation of 0.8 (previous results from (de Bejczy et al., 2015)). Recruiting 320 patients, randomized in 4 groups of 80 each, we get a detectable effect of 0.35 umol/l and a Cohen's d of 0.44. With regards to HDD, we assume that we can use ordinary t-tests based on normal distribution, with $\alpha=0.025$, $1-\beta=0.80$, using a standard deviation of maximum 0.35 (previous results from (Litten et al., 2013)). Recruiting 360 patients, randomized in 4 groups of 90 each, we get a detectable effect of 15% and a Cohen's d of 0.43. Hence, a sample size of approximately 360 patients should be randomized.

Drop-out rate

Based on prior studies (de Bejczy et al., 2015) with similar design and outcome, the drop-out rate is estimated to approx. 20 % between screening and randomization and approx. 6.5% for randomization to subjects included in modified ITT. To balance the drop-out, 380 subjects are estimated for randomization to reach 360 subjects in the modified ITT.

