Additionally, B-PEth-level analysis compared to baseline levels will also be performed for Day7, Day 21, Day 35, Day 49, Day 63 and Day 77. B-PEth has a well-documented declining pattern and hence it follows that the mean value during the treatment period will be a sufficient statistic for the post-treatment level. B-PEth will be collected initially at the screening visit and onwards from randomization visit every 2nd week during the study (except for the first visit, which is one week after randomization). An analysis with regards to B-PEth, will be performed using an analysis of covariance (ANCOVA) using the mean value of B-PEth (day21-day77) within patient, as the dependent variable. Adjustments for following covariates will be performed: treatment group, center, nicotine use (Yes/No) and family history positive, FHP (Yes/No).

The ANCOVA model will have fixed effects for treatment and center and subject, nicotine use and FHP will be entered as random effect.

Baseline B-PEth will be used as a covariate in the analysis.

- **Heavy Drinking Days (HDD)**

The additional main outcome will be alcohol consumption as measured by Heavy Drinking Days (HDD) using the Time Line Follow Back (TLFB) procedure. The number of heavy drinking days HDD by 14 days is defined as a mean over the 8-week steady state active treatment period (Day 21 -Day 77) compared to baseline. A HDD is defined in two ways; as ≥ 60 grams for men and ≥ 40 for women according to EMA's guideline and as ≥ 70 grams for men and ≥ 56 grams for women according to FDA's guideline on the development of medicinal products for the treatment of alcohol dependence. The baseline mean of heavy drinking days by 14 days, is obtained at the screening visit, where the number of heavy drinking days over the last 30 days is registered.

The number of heavy drinking days, "HDD 21-77", is the total number of heavy drinking days divided by 4 (8weeks/2), in order to get a 14 day-period measurement. The maximum total number of days measured is 56 days. Additionally, HDD analysis compared to baseline levels will also be performed for Day7, Day 21, Day 35, Day 49, Day 63 and Day 77 and parts of the 8 week steady state active treatment period.

Adjustment for the covariates treatment group, smoking (Yes/No), family history positive, FHP, (Yes/No) and center will be performed. Baseline alcohol consumption will be used as a covariate in the analysis. The

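### The primary B-PEth ANCOVA adjusts for one unnamed baseline although two pre-dose values exist; entering both as separate covariates costs one degree of freedom and could gain precision

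*Protocol*

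**What the plan says.** Section 8.2 of the protocol analyses B-PEth by ANCOVA. The dependent variable is each patient's mean over Day 21 to Day 77, and "Baseline B-PEth will be used as a covariate in the analysis". The endpoint is also described as a comparison with baseline and as a within-patient difference. No visit is named for that baseline, and no rule is given for combining samples.

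The same section says that "B-PEth will be collected initially at the screening visit and onwards from randomization visit every 2nd week during the study". Section 3.3 puts the randomization visit at most 10 days after screening and has patients take their first dose the next morning. Both samples are therefore pre-dose.

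Other places bear on the point:
- Section 4.1, criterion 5, requires "B-PEth levels of ≥0.5 µmol/L at screening visit (visit 1"). Only the screening value carries this cut-off.
- Section 8.2 does name a visit for the other primary endpoint: the HDD baseline comes from screening.
- Table 2 in section 3.1 puts the word baseline beside Visit 1, but that table sets out time burden, not endpoints.
- The mITT set in section 8.2 requires both pre-dose visits to be completed. The per-protocol set requires valid B-PEth results at both.
- Missing B-PEth values are left missing; only TLFB data are imputed.

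**The concern.** A baseline covariate earns its place by explaining variance in the outcome. Two pre-dose measurements can explain more than one, and here both are already scheduled. Section 8.1 gives a detectable standardised effect of 0.44 on B-PEth, while section 3.2 hypothesises about 0.35 for each single drug, so inexpensive precision is worth having.

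A second matter is interpretation. The hypotheses in section 8.2 speak of reductions from baseline as well as differences between arms. A value on which patients were selected tends to run high and to fall back on re-measurement. The size of a within-arm fall therefore depends on whether screening or Day 0 is the reference, and that choice should not be open once results are known.

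**Working it through.** **1. The plan's own figure.** Section 8.1, "using a standard deviation of 0.8": "Recruiting 320 patients, randomized in 4 groups of 80 each, we get a detectable effect of 0.35 umol/l". Detectable difference = (z_alpha + z_beta) × SD × sqrt(2/n). With alpha 0.025 one-sided and power 0.80: (1.960 + 0.842) × 0.8 × sqrt(2/80) = 0.354 µmol/L, or d = 0.443, with power 0.790 at 0.35. This matches the stated 0.35, 0.44 and 0.80. A two-sided 0.025 would give 0.390, which does not match. The calculation is a t-test with no covariate, so nothing in it depends on the choice of baseline.

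**2. Formulas.** Let r1 and r2 be the correlations of the Day 0 and screening values with the on-treatment mean, and r12 the correlation between the two. Residual variance as a fraction of outcome variance is:
- Day 0 alone: 1 − r1²
- simple mean of the two (equal variances): 1 − [(r1 + r2)/2]² / [(1 + r12)/2]
- both as covariates: 1 − (r1² + r2² − 2·r1·r2·r12)/(1 − r12²)

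**3. Two illustrative cases (assumed correlations).**
- Equal predictors, r1 = r2 = 0.6 and r12 = 0.8. Day 0 alone: 0.640. Mean: 1 − 0.36/0.9 = 0.600. Both: 1 − 0.144/0.36 = 0.600. The cut is 6.2%.
- Pure serial correlation, r1 = 0.6, r12 = 0.8, r2 = 0.6 × 0.8 = 0.48. Day 0 alone: 0.640. Mean: 1 − 0.54²/0.9 = 0.676, a 5.6% increase. Both: 1 − (0.36 + 0.2304 − 0.4608)/0.36 = 0.640, no change.

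At r1 = 0.6 and r12 = 0.8, the mean beats Day 0 alone only if r2 exceeds 0.6 × (sqrt(3.6) − 1) = 0.54. Entering both has no such threshold.

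**4. Range for both covariates.** The outcome is the mean of five visits (Days 21, 35, 49, 63 and 77), and screening is taken 10 days before Day 0. Power is at 80 per arm, difference 0.35 and alpha 0.025 one-sided, taking 0.8 as the residual SD after adjustment for the single baseline. That is an assumption, because section 8.1 does not say whether 0.8 is raw or residual. The reference power is 79%.

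| Assumed structure | Variance cut v Day 0 alone | Variance cut v screening alone | Power v Day 0 | Power v screening |
|---|---|---|---|---|
| Pure serial, 14-day correlation 0.6–0.9 | 0% | 5–16% | 79% | 81–86% |
| Stable component (0.4 or 0.6) plus serial part (0.7 or 0.85) plus 5% or 15% measurement error | 3–12% | 12–20% | 80–84% | 84–87% |
| Equal correlation 0.5–0.9 at all visits | 24–39% | 24–39% | 89–94% | 89–94% |

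The samples are at most 10 days apart and section 3.4 puts the PEth half-life at about one week, so some serial decay is to be expected. The equal-correlation row is therefore an upper bound rather than a central case.

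**5. Screening cut-off.** A lognormal simulation with patients kept only if screening was at least 0.5 µmol/L gave cuts of 0% to 28% against Day 0 and 10% to 29% against screening. The high ends come from equal correlation at 0.7, and the low ends from serial correlation at 0.8.

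**6. Cost.** One extra parameter among the 360 mITT patients of section 8.1 is of the order of 1/360, about 0.3% of residual variance.

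**The case against.** Section 8.2 refers statistical detail to a separate SAP, which was not available for this review. Naming the baseline visit is ordinary SAP content. That stands: the unnamed visit alone would not be a point, and the term used does not even exclude a two-visit definition. What remains is the method. Using both collected values as covariates is better than using either one, whichever visit the SAP names.

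ANCOVA with one baseline covariate is also standard and valid, and the gain may be nil. Both parts stand. If Day 0 is the intended baseline and serial correlation dominates, the screening value adds nothing.

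Three stronger readings are tempting, and the documents support none of them:
- A reader might infer that averaging the two values is bound to cut residual variance at no cost. The second case in step 3 shows the mean raising it by 5.6%. Averaging would also carry the selected screening value into the change from baseline.
- A reader might infer that half the pre-treatment information is wasted. Two samples taken within 10 days overlap heavily, so the second adds far less than half.
- A reader might infer that selection on screening B-PEth biases the treatment comparison. Selection precedes randomization and applies to all arms alike.

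**Conclusion.** The point holds as a low-cost improvement, not as an error. Entering both pre-dose values cannot raise residual variance beyond the loss of one degree of freedom. The gain is about 0% to 12% against Day 0 alone and about 5% to 20% against screening alone under the assumed serial structures, and more under equal correlation. No narrower range can be given, because the protocol reports no within-patient correlations.

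The stakes are modest. The trial plans 90 per arm in the mITT, where the detectable d under the section 8.1 inputs is 2.802 × sqrt(2/90) = 0.418. A 12% cut would bring it to 0.418 × sqrt(0.88) = 0.39, and a 20% cut to 0.418 × sqrt(0.80) = 0.37. Both stay above the hypothesised 0.35 for a single drug. The planned sample size is unaffected.

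The choice of reference visit matters for within-arm falls from baseline, where regression to the mean after selection at 0.5 µmol/L could add to the apparent reduction if screening is used.

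**What to change.** In section 8.2 or the SAP, before unblinding:
- Enter screening B-PEth and Day 0 B-PEth as two separate covariates in the primary ANCOVA. Do not replace them by their mean.
- If one pre-dose sample fails, use the available value in its place so that the patient stays in the model. Write this as an explicit exception to the rule that missing B-PEth is not imputed.
- State which value defines the change from baseline, and note that the screening value is subject to the eligibility cut-off. With both values in the model, the between-arm contrast is the same whichever is subtracted, so this choice affects only the within-arm description.

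The cost is one or two sentences and one degree of freedom. No new samples, visits or patients are needed.

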Primary objective: To assess the effects of varenicline and bupropion in combination and alone for reducing alcohol consumption in individuals with AUD.

Two primary efficacy end-points will be used.

- 1) Alcohol consumption as measured by the objective alcohol marker B-PEth
- 2) Alcohol consumption as measured by heavy drinking days (HDD*) by using the Time Line Follow Back (TLFB) procedure

*HDD is defined as ≥ 60 grams for men and ≥ 40 for women according to EMA's guideline and as ≥ 70 grams for men and ≥ 56 grams for women according to FDA's guideline on the development of medicinal products for the treatment of alcohol dependence.

Secondary objectives:

- 1) To assess the effects of varenicline and bupropion in combination and alone for reducing alcohol consumption in individuals with AUD by using
 - The indirect alcohol marker carbohydrate deficient transferrin (CDT)
 - The indirect alcohol marker gamma glutamyltransferase (GGT)
 - Self-reported alcohol consumption as measured by TLFB:
 - Mean grams of alcohol per day
 - Number of drinking days
 - Number of drinks per drinking day
 - Number of abstaining days
- 2) Total score of Alcohol Use Identification Test (AUDIT)
- 3) Alcohol craving as measured by a Visual Analogue Scale (VAS)
- 4) Nicotine use measured by the nicotine saliva marker cotinine
- 5) Temporal Experience of Pleasure Scale (TEPS)
- 6) The Continous Performance Test + Activity test (CPTA)
- 7) To assess the relationships between the above described outcome measures and plasma drug concentrations of bupropion and varenicline

Study design overview: A 13-weeks (91 days) multicenter, placebo-controlled, randomized, double-blind clinical trial with four parallel groups.

Development phase: II

Number of randomized subjects: 380 subjects with AUD. 95 subjects per treatment arm will be randomized into the study.

Number of sites: 5 sites in Sweden

Inclusion criteria

- 1) Signed informed consent
- 2) Blood alcohol level below <0.1‰ (0.1 g/L) at signing informed consent
- 3) 25-70 years of age at screening
- 4) Moderate and severe AUD according to DSM-V (meeting ≥4 out of 11 criteria)
- 5) B-PEth levels of ≥0.5 µmol/L at screening visit (visit 1)
- 6) Continuous high alcohol consumption over the last 3 months prior to screening as defined by at least 2 HDD per week on a typical week.
- 7) Available phone number for contact
- 8) Ability to speak and write in Swedish

Exclusion criteria

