ID control is performed and breath alcohol level is determined to ensure sobriety (defined as blood conc. <0.1%). The participant may be offered a new screening visit, e.g. the following day, if sobriety is not fulfilled. Before any trial-related examination is performed, informed consent will be obtained. The subject will be informed orally of the aim of the trial, what participation entails and will be supplied with written information summarizing the details of the trial to read. Ample time will be given to the subjects to consider their participation. Agreement to participate in the trial will be confirmed by the subject signing and dating the Informed Consent Form (ICF). Documentation of the procedure is confirmed by delegated site personnel signing and dating the ICF. Medical history and alcohol anamnesis are collected and a physical examination is performed. Vital signs, safety and outcome specific blood samples and urine samples for pregnancy and toxicology will be collected. Alcohol consumption 30 days back in time will be documented by using the TLFB procedure. Baseline information is collected; demographics, alcohol and nicotine history, depression, and ADHD. The AUDIT and DUDIT will be administered. The Temporal Experience of Pleasure scale (TEPS) will be administered, and the Continuous Performance Test + Activity (CPTA) attention test will be performed via iPod. The eligibility criteria (except B-Peth criteria) will be evaluated by the medical doctor. If non-eligible and if required by medical condition the study seeking subject may be referred to appropriate clinic. If eligibility criteria are fulfilled, the subjects will be invited to a second visit within 8 days for randomization.

- Perform BrAC test by alcometer measuring alcohol concentration in exhaled air.
- ID control
- Perform the informed consent procedure, written and orally, confirmed by the subject signing and dating the ICF.
- Collection of medical history
- Collection of alcohol anamnesis and confirmation of alcohol diagnosis.
- Complete TLFB Alcohol calendar for 30 days preceding screening visit
- Collect AEs, if any
- Collect concomitant medication, if any
- Perform physical examination, which includes examination of armpits (lymph nodes), examination of mouth and throat, auscultation of heart and lungs, and palpitation of abdomen.
- Collect vital signs: Blood pressure and heart rate (after 10 min rest), length (at visit 1 only) and weight (at visit 1 and visit 9)

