- Draw blood for safety parameters, AST, ALT, PC, glucose, creatinine, Na+/K+, Hb, LPK, TPK and hsCRP
- Draw blood for efficacy parameters B-PEth, CDT and GGT
- Perform dip stick tests for U-tox and U-hCG (pregnancy status, females only)
- Collect demographic data
- Complete questionnaires: VAS craving, AUDIT, DUDIT, ASRS, MADRS, Alcohol quantity frequency, nicotine quantity frequency and TEPS
- Administer CPTA test via iPod.
- Control and confirm (except B-Peth criteria) eligibility

Visit 2. Randomization Visit. Accepted range: Maximum 10 days from screening visit

The eligibility criteria based on blood sample analysis are checked and signed by medical doctor. If non-eligible and if required by medical condition the study seeking subject may be referred to appropriate clinic. The eligibility criteria are again confirmed. Medical status and concomitant medication is checked if case status has changed since screening. Data on alcohol consumption since last visit is collected by TLFB. Vital signs and blood samples for outcome specific measurements are collected. Urine sample for pregnancy and toxicology are collected. The subject is randomized to the trial and patient emergency card is handed out.

Saliva sample is collected for cotinine (nicotine metabolite) determination. The IMP is distributed according to randomization list. Patient emergency card is handed out. The study participants will be instructed to start taking the study drug on the following morning, the day after the randomization visit.

Before randomization

- Perform dip stick tests for U-tox, and pregnancy status (if applicable)
- Collect vital signs: Blood pressure, heart rate (after 10 min rest)
- Complete TLFB alcohol calendar since last visit
- Administer VAS craving questionairre
- Check and confirm that medical status is unchanged since screening visit
- Check and confirm eligibility criteria in eCRF system (in order to do this, all above measures must be entered in eCRF)
- Randomization
- Distribute patient emergency card
- Collect concomitant medications if any
- Collect AEs if any
- IMP distribution
- Perfrom saliva dip stick test for cotinine determination
- Collect blood for B-PEth, CDT and GGT analyses

Visit 3. Core battery visit. Accepted range +/- 3 days from scheduled visit date

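### The HDD baseline leaves out the pre-dose drinking days from screening to Day 0, which gives up a modest amount of precision on a primary endpoint

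*Protocol*

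**What the plan says.** Protocol section 8.2, under Heavy Drinking Days, ties the baseline to one source: "The baseline mean of heavy drinking days by 14 days, is obtained at the screening visit, where the number of heavy drinking days" over the preceding 30 days is recorded. Section 3.3 has the matching task at Visit 1: "Complete TLFB Alcohol calendar for 30 days preceding screening visit". Baseline consumption is then a covariate in the HDD ANCOVA.

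Section 3.3 also collects the calendar at Visit 2: "Data on alcohol consumption since last visit is collected by TLFB". This task is listed among those done before randomisation, and subjects are told to "start taking the study drug on the following morning, the day after the randomization visit". Every day from screening to Day 0 is therefore both pre-randomisation and pre-dose.

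The length of that window is given in two ways in section 3.3. The Visit 2 heading says "Accepted range: Maximum 10 days from screening visit", while the Visit 1 text says "the subjects will be invited to a second visit within 8 days for randomization". No minimum is given.

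The screening-to-Day 0 days do have other uses. Section 4.2 excludes subjects who did not drink at all in that interval, and section 8.2 makes a completed Day 0 calendar one of the per-protocol milestones. They have no role in the HDD baseline.

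**The concern.** The days between screening and Day 0 are the last drinking days before treatment, and they follow consent and the screening work-up. If subjects change their drinking on entering the trial, if that change differs between subjects, and if it lasts, these days predict drinking in Day 21-77 better than the earlier 30 days alone. Even without an entry effect, they are extra observations closer in time to the outcome window.

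A baseline that omits them leaves this predictable variation in the residual of every HDD contrast. What is at stake is the width of the confidence intervals on one of the two primary endpoints, using data that the trial already collects.

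**Working it through.** **1. The plan's own figure.** Section 8.1 gives SD 0.35, difference 0.15, alpha 0.025, power 0.80 and 90 per arm, using unadjusted t-tests.

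- SE = 0.35 × √(2/90) = 0.0522, and 0.15/0.0522 = 2.875.
- With alpha 0.025 one-sided, power = Φ(2.875 − 1.960) = 0.820. The detectable difference is (1.960 + 0.842) × 0.0522 = 0.146, which rounds to the stated 15%.
- With alpha 0.025 two-sided, power = Φ(2.875 − 2.241) = 0.737.

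The stated size therefore reproduces with a one-sided 0.025, which is used below. It takes no credit for any covariate. The model's outcome is the 56-day total divided by 4, which is 14 times the proportion. Relative variances and power are the same on both scales.

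**2. Effect of a second covariate.** Adjusted SD = 0.35 × √(1 − R²). The protocol gives no baseline-to-outcome correlation, so R² was computed from an assumed day-level model. The model has a stable subject trait (variance t), a state that decays over τ days (variance s) and daily noise (variance e). It compares the 30-day baseline alone with the 30-day baseline plus a separate screening-to-Day 0 rate. The last row is a purely stable trait.

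| Window (days) | t, s, τ, e | r, 30 days only | Multiple r, both | Residual variance ratio | Power, 15 points | Power, 10 points |
|---|---|---|---|---|---|---|
| 4 | 0.1, 0.2, 14, 0.7 | 0.494 | 0.512 | 0.976 | 0.911 → 0.917 | 0.596 → 0.607 |
| 8 | 0.1, 0.2, 30, 0.7 | 0.488 | 0.529 | 0.945 | 0.909 → 0.923 | 0.593 → 0.618 |
| 10 | 0.05, 0.3, 60, 0.65 | 0.462 | 0.534 | 0.909 | 0.900 → 0.925 | 0.580 → 0.621 |
| 10 | 0.3, 0.3, 60, 0.4 | 0.712 | 0.753 | 0.877 | 0.983 → 0.992 | 0.779 → 0.830 |
| 10 | 0.4, about 0, any, 0.6 | 0.963 | 0.969 | 0.846 | 1.000 → 1.000 | 1.000 → 1.000 |

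The second row, in full: (1 − 0.529²)/(1 − 0.488²) = 0.720/0.762 = 0.945. Across the main settings the cut is about 2-12%. In the stable-trait limit it is 7-15%. A 2-12% cut narrows a confidence interval by 1 − √0.98 = 1% to 1 − √0.88 = 6%. Pooling the extra days with the 30 days, instead of entering them separately, gives less: about 1-9%.

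**3. Adding a change at study entry.** A second assumed model used a subject-level logit HDD probability (SD 1.2), selection at 2 or more HDD per week and an entry shift of mean −0.7 that persists into the outcome window. Later drift had SD 0.6-1.0 and windows were 4 to 8 days. The cut in residual variance depends on how much the entry shift varies between subjects:

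- shift SD 0: 1-5%
- shift SD 0.4: 4-14%
- shift SD 0.7: 12-30%
- shift SD 1.0: 23-45%

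With unequal windows and a strong weekday pattern added, the cuts were about 1.5-5% at SD 0 and 4.5-14% at SD 0.4.

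**4. Bias.** In a binary-day simulation with selection and a common drop after screening, the between-arm estimate under no effect was within 0.0012 of zero with either baseline. Bringing in the extra days lowered the standard error by about 2-4%.

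**The case against.** The 30-day baseline is a sound choice. It is pre-randomisation and pre-specified, it covers four full weeks and so balances weekdays, and it enters as a covariate. Section 8.2 defers detail to an SAP that was not part of this check, and nothing in the protocol bars a second drinking term. The extra window is short, has no minimum length and is itself selected, because complete abstainers are removed. These patients drink by weekday, as the imputation rule in section 8.2 recognises, so a short window partly reflects when the visit was booked. At four days each heavy day moves the covariate by 14/4 = 3.5 HDD. The 30 days may also hold part of any entry effect, since section 3.3 allows screening up to 14 days after pre-screening. All of this stands. It limits the gain but does not reverse it: every setting examined showed some reduction.

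Three stronger readings are tempting and are not supported.

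- *Selection biases the treatment comparison.* Inclusion criterion 6 in the Synopsis reads "Continuous high alcohol consumption over the last 3 months prior to screening as defined by at least 2 HDD per week on a typical week", so the 30 days are only part of the selection period. Regression to the mean also acts alike in all randomised arms. It can inflate within-arm reductions from baseline, but a second covariate would not cure that.
- *The loss is as large as 12-30% or more.* That needs large, persistent entry shifts that differ between subjects, and the protocol gives no such figure. The placebo response described in section 1.1 comes from a diary in an earlier trial. It is an average shift and says nothing about variation between subjects.
- *The trial is underpowered because of this.* The sample size uses unadjusted tests and does not rely on the baseline at all.

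**Conclusion.** Section 8.2 makes a valid but slightly inefficient choice of HDD baseline. It is not an error, and the randomised comparison is unbiased with either baseline. The precision given up is modest: about 2-12% of residual variance under the assumed day-level models and 1-5% if entry shifts do not vary between subjects. Larger losses occur only if those shifts are large and last. At 90 per arm and a 15-point difference this is worth at most about 2.5 power points, and up to about 5 points at a 10-point difference. The direction is secure. The size rests on assumed correlations, because the protocol reports none. The planned sample size is unaffected.

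**What to change.** Add one sentence to section 8.2, or to the SAP if it does not already have it, before unblinding. For example: *Two baseline covariates enter the HDD ANCOVA: HDD per 14 days over the 30 days before screening (count × 14/30), and HDD per 14 days from screening to Day 0 (count ÷ days observed × 14), both using the same gram threshold as the outcome.*

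Dividing by days observed deals with unequal windows. A rule for a missing Visit 2 calendar is also needed and should use pre-randomisation data only. The 8-day and 10-day statements in section 3.3 should be reconciled.

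No new data are needed. The cost is one degree of freedom, and a noisier covariate when the window is short or covers few weekend days. That noise reduces the gain but cannot bias the randomised contrast.
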